1. INTRODUCTION

Loss of pancreatic beta-cell mass is a key factor in Type 1 Diabetes (T1D), but therapies to halt this process are not available. The investigators have discovered thioredoxin-interacting protein (TXNIP), as a promising target in this regard and have now found that the commonly used anti-hypertensive drug and calcium channel-blocker, verapamil, effectively lowers beta-cell TXNIP expression in rodent beta-cells and human islets, promotes beta-cell survival and rescues mice from T1D. This makes verapamil a potentially attractive drug for T1D, but prospective clinical data are lacking. The investigators primary objective is therefore to conduct a randomized, placebo-controlled, double-blind study of the efficacy and safety of verapamil in adults with recent-onset T1D and to demonstrate that subjects on oral verapamil daily for 12 months will have improved insulin production (as an indirect measure of beta-cell mass). Results will have major translational implications with potential immediate impact on clinical care, encourage large clinical follow-up trials, evaluate markers of beta cell health and ultimately help develop a novel therapy that enhances the patient's own beta-cell mass and function.

2. STUDY OBJECTIVES

The overall purpose of this trial is to assess the efficacy and safety of using oral verapamil in subjects with recent onset T1D in order to downregulate TXNIP and enhance the patients' endogenous beta cell mass and insulin production. The objectives are therefore to assess parameters of beta cell survival (including new biomarkers), insulin production and glucose control and the feasibility of this approach and thereby provide the basis for future, larger/expanded, longer-term verapamil studies and the off-label use of this approved drug for T1D.

3. STUDY DESIGN

3.1 General Design

The trial is designed as a double-blind placebo-controlled study. Participants will be randomized in a 1:1 ratio, through a simple randomization approach using computer-generated random numbers, to receive oral verapamil or match placebo in addition to standard care with continuous subcutaneous insulin infusion via an insulin pump.

3.2 Primary Outcome

Functional Beta Cell Mass as determined by the area under the curve (AUC) from a 2-hour mixed meal stimulated C-peptide after daily verapamil for 12 months. A greater improvement in insulin production (as an indirect measure of beta cell mass) in subjects receiving verapamil as compared to those receiving placebo would provide an indication of the efficacy of the intervention.

3.3 Secondary Outcomes

1. Exogenous Insulin Requirements at 3 and 12 months

Exogenous insulin requirements as assessed by mean daily insulin use over 7-14 consecutive days. The percent change from baseline will be assessed as a surrogate inverse marker of residual beta cell function.

2. Glycemic Control at 3 and 12 months

Glycemic control, as measured by HbA1c and hypoglycemic events. In addition to being an important determinant of residual beta cell function/survival, it also helps reveal a more complete picture of beta cell function.

3.4 Other Outcome Measures

Beta cell markers at 3 and 12 months

We will collect serum at baseline and Months 3, 6, 9, 12 for future assessment of putative beta cell markers.

4. SUBJECT SELECTION AND WITHDRAWAL

4.1 Inclusion Criteria

Subjects must meet all of the following criteria:

- A. Diagnosis of Type 1a Diabetes Mellitus based on ADA Criteria
- B. Written informed consent obtained from the subject including consent for the use of research-related health information
- C. ≥ 18 years of age and ≤ 45 years of age
- D. < 3 months since T1DM was diagnosed
- E. BMI < 30
- F. Baseline A1c $< 10\%$
- G. Detectable fasting or stimulated C-peptide level (above the lower limit of detection of the assay)
- H. C-peptide increase during screening mixed meal tolerance test with a minimal stimulated value of ≥ 0.2 pmol/mL
- I. Presence of antibodies to at least one of the following antigens: insulin, GAD-65, IA-2, or Znt8
- J. Agree to intensive management of diabetes with an HgbA1c goal of $< 7.0\%$ and willing to wear and insulin pump and CGMS
- K. If female, (a) surgically sterile or (b) postmenopausal or (c) if of reproductive potential, willing to use medically acceptable birth control (e.g. female hormonal contraception, barrier methods or sterilization) until 3 months after completion of any Treatment Period
- L. Serum creatinine $\leq 1.5 \times$ upper limit of normal (ULN)
- M. Currently receiving insulin therapy
- N. Willing to forego other forms of experimental treatment during the study

4.2 Exclusion Criteria

Subjects must have none of the following:

- A. Any medical condition that, in the opinion of the investigator, would interfere with safe completion of the trial
- B. Pregnant females or lactating females who intend to provide their own breast milk to the baby during the study
- C. Current therapy with GLP-1 receptor agonists, pramlintide, or any other agents that might be thought to potentially stimulate pancreatic beta cell regeneration or insulin secretion
- D. Current treatment with oral antidiabetic agents
- E. Uncompensated heart failure, fluid overload, myocardial infarction or evidence of ischemic heart disease or other serious cardiac disease as described in New York Heart Association (NYHA) Class III or IV criteria within the 12 weeks before randomization

- F. History of epilepsy, cancer, cystic fibrosis, sickle cell anemia, neuropathy, peripheral vascular disease or cerebrovascular disease
- G. Untreated hypothyroidism or active Graves' disease with hyperthyroidism
- H. Treatment with systemic glucocorticoid therapy by oral, intravenous (IV), or intramuscular (IM) route within 12 weeks before randomization; patients who are likely to require treatment with corticosteroids during the trial are also excluded
- I. Evidence of active infection
- J. Total bilirubin $> 1.5 \times$ upper limit of normal (ULN)
- K. Aspartate aminotransferase (AST) or alanine aminotransferase (ALT) $> 1.5 \times$ ULN
- L. A psychiatric or medical disorder that would prevent giving informed consent
- M. Hypersensitivity to verapamil or any component of the formulation; known left ventricular dysfunction; hypotension (systolic pressure < 90 mm Hg); PR interval prolongation on EKG or any bradydysrhythmia (e.g. sick sinus syndrome, AV block); atrial flutter or fibrillation, and an accessory bypass tract (Wolff-Parkinson-White [WPW] syndrome, Lown-Ganong-Levine syndrome)

4.3 Recruitment and Screening

Subjects who are 18-44 years of ages and diagnosed with T1D within the previous 3 months will be screened with mixed-meal tolerance test (MMTT) for the presence of a minimal stimulated C-peptide value of ≥ 0.2 nmol/L and at least one positive T1D associated antibody.

4.4 Early Withdrawal of Subjects

Subjects will be considered withdrawn if they stop participating in the study or withdraw consent. Subjects are not required to state their reasons for withdrawing consent. Subjects will be withdrawn if, in the investigator's opinion, continuation in the study would be detrimental to their well-being.

5. STUDY DRUG

Verapamil SR or Placebo

1st month 120mg daily, 2nd month 240mg daily, 3rd-12th month 360mg daily

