6. STUDY PROCEDURES

To assess the primary endpoint of beta cell function as determined by the stimulated C-peptide AUC, mixed meal tolerance tests (MMTT) will be performed at 0, 3 and 12 months as previously described (Diabetes Care 31, 1966-1971, 2008). The MMTT will only be performed when fasting blood glucose levels are within the range of 3.9-11.1 mmol/L, otherwise the test will be rescheduled. Blood samples will be collected at -10, 0, 15, 30, 60, 90 and 120 min for serum C-peptide analysis. The C-peptide AUC (0-120min) will be divided by the time of the test to obtain the mean AUC (in nmol/L).

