8. SAFETY

Participants will be seen monthly during the first three months and then every 3 months until the end of the study, and will be carefully monitored for any occurrence of hypotension, bradycardia, or EKG changes (PR- or QT- interval prolongation).

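### Verapamil rises to 360 mg by study month with no dose action tied to the monitored blood-pressure and EKG findings, and the plan does not say whether follow-up continues after drug is stopped

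*Combined protocol and SAP*

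**What the plan says.** Section 5 is the whole of the dosing plan: "1st month 120mg daily, 2nd month 240mg daily, 3rd-12th month 360mg daily".

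Section 8 sets the visits: "Participants will be seen monthly during the first three months and then every 3 months until the end of the study". Participants are to be "carefully monitored for any occurrence of hypotension, bradycardia, or EKG changes (PR- or QT- interval prolongation". No limit is given for any of these findings, and no consequence for the dose.

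Section 4.4 holds the only stopping text. It defines withdrawal, "Subjects will be considered withdrawn if they stop participating in the study or withdraw consent", and adds one clause on harm: "Subjects will be withdrawn if, in the investigator's opinion, continuation in the study would be detrimental to their well-being". It does not mention stopping, holding or reducing study drug.

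Exclusion criterion M in Section 4.2 bars entry for, among other conditions, "hypotension (systolic pressure < 90 mm Hg); PR interval prolongation on EKG or any bradydysrhythmia". These conditions are not repeated as limits during treatment.

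Section 6 states that "mixed meal tolerance tests (MMTT) will be performed at 0, 3 and 12 months" and does not make the tests depend on being on drug. Section 3.2 words the primary outcome as "stimulated C-peptide after daily verapamil for 12 months".

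**The concern.** The main issue is safety, which Section 2 makes part of the trial's purpose. Section 1 describes verapamil as an anti-hypertensive, and Section 4.1 does not require participants to have hypertension, so low blood pressure on treatment is foreseeable. The protocol treats low systolic pressure, PR prolongation and bradydysrhythmia as reasons to keep a person out, but does not say what to do when one of them appears on drug. The written options are the scheduled dose or withdrawal from the study. Anything in between rests on unwritten judgement, which can differ from one participant to the next.

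The second issue is the primary outcome. A participant withdrawn for one of these findings may have no 12-month C-peptide AUC. Section 8 singles these findings out for monitoring in a trial of this drug, so losses could differ between arms. Section 7 names no analysis set and no method for missing values that would deal with this.

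**Working it through.** The plan states no figure on this point to reproduce. It gives no sample size, event rate or dropout rate. The check is a reading of the sections side by side, plus simple arithmetic on the schedule.

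**Inputs.** Doses by study month: 120, 240, then 360 mg for months 3 to 12 (Section 5). Visits, as read from Section 8: months 1, 2, 3, 6, 9 and 12. Meal tests: months 0, 3 and 12 (Section 6).

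**1. Dose steps.** There are two, 120 to 240 mg and 240 to 360 mg. The month-1 and month-2 visits fall at these steps, but no text makes a step depend on what the visit finds. Steps with a safety condition: 0 of 2.

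**2. Time at the top dose.** 10 of 12 months are at 360 mg. Planned exposure is 120 + 240 + 360 × 10 = 3960 mg/day × months, of which 3600/3960 = 90.9% is at 360 mg. After the month-3 visit, the remaining 9 months have visits every 3 months. This describes the schedule; all 12 months lack an action rule.

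**3. Meal tests lost on withdrawal from the study.**

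| Withdrawal | Post-baseline tests available | 12-month primary value |
|---|---|---|
| Month 1 or 2 | 0 of 2 | No |
| After the month-3 test, before month 12 | 1 of 2 | No |

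A participant who stops drug but stays in the study is a different case. Section 4.4 does not class that person as withdrawn, and Section 6 does not exclude them from testing. The plan does not say which course applies.

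**4. Exposure if a dose rule is applied.** The planned mean is 3960/12 = 330 mg/day. The documents give no rate, so take 15% of the verapamil arm affected as an assumption, against 0% (no change). Arm mean = 0.85 × 330 + 0.15 × individual mean = 280.5 + 0.15 × individual mean.

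| Action for the affected 15% | Individual mean (mg/day) | Arm mean (mg/day) | Change |
|---|---|---|---|
| Held at 240 mg | (120 + 240 × 11)/12 = 230 | 315 | −4.5% |
| Held at 120 mg | 120 | 298.5 | −9.5% |
| Stopped at month 1 | 120/12 = 10 | 282 | −14.5% |
| Stopped at month 6 | (120 + 240 + 360 × 4)/12 = 150 | 303 | −8.2% |
| Reduced to 240 mg at month 9 | (120 + 240 + 360 × 7 + 240 × 3)/12 = 300 | 325.5 | −1.4% |

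These changes are against everyone completing the full schedule, so they are not the added cost of a rule. Someone withdrawn at month 1 under Section 4.4 also averages 10 mg/day over the year; being held at 120 mg instead would raise that person's exposure.

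**5. Dilution.** If a proportion p stop drug and keep none of its effect (assumption), the randomised-arm difference is (1 − p) of the full-adherence effect: 100% at p = 0 and 1 − 0.15 = 85% at p = 0.15.

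**The case against.** The best defence is that participants are protected already. Section 4.4 is mandatory once the investigator judges harm. Monthly visits coincide with the period when the dose rises. Exclusion criteria A, E and M remove people with serious cardiac disease, hypotension or conduction problems. This is a brief protocol whose sample size draws on guidance for pilot studies, so fixed thresholds may be thought unnecessary. All of that stands as fact, and a reader who inferred that nothing can stop dosing in a participant who is being harmed would be wrong. What the defence does not supply is a common limit or any written step between the scheduled dose and withdrawal from the study.

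A reader might also infer that the plan forbids a hold, or that anyone who stops drug loses the remaining meal tests. The text supports neither. A hold is unaddressed, and the tests are not conditional on treatment. Nor is there a basis here for faulting the absence of an off-drug test after month 12.

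Lastly, analysing people who stopped drug in their randomised arm moves away from the wording in Section 3.2 of an outcome after 12 months of daily verapamil, and it dilutes the effect. In a trial looking for an early efficacy signal that is a real cost. It has to be weighed against losing the primary value in participants who leave for safety reasons.

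**Conclusion.** The concern holds as a gap in the written dosing and follow-up rules. Escalation to 360 mg is unconditional, no dose action is linked to the findings in Section 8, and withdrawal from the study is the only written response to harm. On follow-up after stopping drug, the plan is silent.

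The size is limited to what the schedule shows: neither dose step is conditional, and a participant withdrawn before month 12 may contribute no primary value. It is tempting to go further and claim a biased treatment effect. The documents give no event rate by arm and no dropout rate, so neither the size nor the direction of any bias can be established. They also give no basis for saying that the dose reached would go unreported.

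The conclusion assumes that no dose-modification rule exists in a document not supplied; the text refers to none. The change is advisable because it is cheap and uses conditions the protocol already treats as unsafe at entry. Investigator-judged withdrawal remains as a backstop.

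**What to change.** **Section 5.** Take each dose step only after blinded review of that visit's blood pressure, heart rate and EKG, with the same rule in both arms. If systolic pressure is below 90 mm Hg, or PR prolongation or a bradydysrhythmia including AV block is present, do not step up, and reduce or stop study drug. Set limits in advance for simple bradycardia and QT prolongation, which Section 8 monitors but exclusion criterion M does not clearly list. Apply the rule at every scheduled visit to month 12.

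**Section 4.4.** Separate stopping study drug from leaving the study. Participants who stop or reduce drug complete the 3- and 12-month meal tests unless they withdraw consent, and are analysed in their randomised arm. Record the dose reached and the reason for any change.

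**Cost.** A short amendment and no added visits. An EKG becomes explicit at months 1, 2, 3, 6, 9 and, if wanted, 12: about 5 to 6 per participant. Section 8's monitoring already implies EKGs but does not fix them to particular visits. Exposure would be somewhat lower, partly offset because some of the same participants would otherwise be withdrawn. The randomised-arm comparison accepts the dilution shown in the working, which should be acknowledged beside the Section 3.2 outcome.

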6. STUDY PROCEDURES

To assess the primary endpoint of beta cell function as determined by the stimulated C-peptide AUC, mixed meal tolerance tests (MMTT) will be performed at 0, 3 and 12 months as previously described (Diabetes Care 31, 1966-1971, 2008). The MMTT will only be performed when fasting blood glucose levels are within the range of 3.9-11.1 mmol/L, otherwise the test will be rescheduled. Blood samples will be collected at -10, 0, 15, 30, 60, 90 and 120 min for serum C-peptide analysis. The C-peptide AUC (0-120min) will be divided by the time of the test to obtain the mean AUC (in nmol/L).

7. STATISTICAL PLAN

Participants' demographic characteristics and outcomes will be summarized as mean and standard errors for continuous variables, and frequency and proportion for categorical variables. The group comparison of baseline measures will be conducted with chi-square test, Fisher's exact test or Student's *t* test where appropriate. The normal distribution assumption will be checked with Q-Q plots. All tests will be two sided. For the primary and secondary outcomes, a repeated-measures two-way ANOVA will be

conducted first; then, where appropriate, the ANCOVA model controlling for the baseline will be conducted to compare group means at the 3- or 12-month time points.

Sample-size estimates are based on the primary outcome of endogenous beta cell function according to stimulated C-peptide AUC, on previously reported sample-size considerations for studying treatment effects on beta cell function at 12 months in newly diagnosed patients with T1D who were older than 18 years in the T1D Trial Network (PLoS One 6, e26471, 2011), and on recommendations for planning pilot studies in clinical and translational research (Clin. Transl. Sci. 4, 332–337, 2011).

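### Section 7 names no analysis population and no method for missing MMTTs, so its month-12 C-peptide comparison rests by default on participants with an observed month-12 test

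*Combined protocol and SAP*

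**What the plan says.** Section 7 gives the analysis in two steps. First: "For the primary and secondary outcomes, a repeated-measures two-way ANOVA will be" conducted. Then, where appropriate, "the ANCOVA model controlling for the baseline will be conducted to compare group means at the 3- or 12-month time points". It gives no estimation method for the ANOVA, and neither it nor any other section names an analysis set, an imputation method, a missing-data assumption or a sensitivity analysis.

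Section 6 fixes the data available: "mixed meal tolerance tests (MMTT) will be performed at 0, 3 and 12 months", so there are two post-baseline values per participant. A test is done only when fasting glucose is "within the range of 3.9-11.1 mmol/L, otherwise the test will be rescheduled". No time window is given, and nothing is said about a test that is never obtained.

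Section 3.2 words the primary outcome as "mixed meal stimulated C-peptide after daily verapamil for 12 months". Section 4.4 states: "Subjects will be considered withdrawn if they stop participating in the study or withdraw consent". It also provides for withdrawal by the investigator for the participant's well-being. It does not separate stopping study drug from leaving the study. Sections 6 and 8 schedule tests and visits without reference to drug use.

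**The concern.** An ANCOVA of month-12 AUC on baseline needs a month-12 value from each participant it includes. With no imputation planned, those without one fall out. The ANOVA run first does not repair this: fitted in the classical way, it drops anyone missing any of the three tests. A participant who gave baseline and month-3 values and then left would contribute nothing to the primary comparison.

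Two things are at stake. If the reasons for loss relate to C-peptide and differ by arm in rate or in kind, the completer comparison is biased. And with the population, the model and the off-drug rule all open, each could be settled after the data are seen. The second problem needs no particular dropout rate to be real.

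The point concerns C-peptide AUC. Section 7 applies the same models to insulin use and HbA1c, but those measures do not depend on an MMTT.

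**Working it through.** **Figures in the plan.** None can be reproduced: the documents state no sample size, SD, effect size, significance level or dropout rate. What follows is an illustration on assumed inputs, with no true treatment effect.

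**Assumptions.** 15 to 30 participants per arm; baseline-to-month-12 correlation ρ = 0.5 or 0.7; adjacent-visit correlation √ρ; correlation r = 0.6 between the tendency to stay and the relevant residual (month 3 or month 12, given baseline); low values more likely to leave. Loss is written verapamil v placebo, and the sign reverses if placebo loses more.

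**Selection factor.** If a fraction f leaves, the mean of the standardised tendency to stay among those remaining is k(f) = φ(z_f)/(1−f), so k(0.10) = 0.195, k(0.20) = 0.350, k(0.30) = 0.497 and k(0) = 0.

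**Loss linked to the month-3 value.** Large-sample completer bias = r × √(ρ(1−ρ)) × [k(f1) − k(f0)].
- ρ = 0.5: multiplier 0.6 × 0.5 = 0.300. 20% v 10%: 0.300 × 0.155 = 0.046 SD. 30% v 0%: 0.300 × 0.497 = 0.149 SD.
- ρ = 0.7: multiplier 0.6 × 0.458 = 0.275. 20% v 10%: 0.043 SD. 30% v 0%: 0.137 SD.

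In simulation the likelihood estimate, which uses the month-3 values of those who leave later, has bias within 0.01 SD if all loss follows the month-3 test. If half the loss comes before that test, its bias is 0.01–0.06 SD. If all of it does, the bias is 0.04–0.15 SD, the same as for completers. Early loss is plausible, because all dose steps in Section 5 fall within the first three months.

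**Loss linked to the unobserved month-12 value.** Completer bias = r × √(1−ρ²) × [k(f1) − k(f0)]. At ρ = 0.5 the multiplier is 0.6 × 0.866 = 0.520, so 30% v 0% gives 0.258 SD. For 30% v 0% with all loss after month 3, simulation over both ρ gives 0.21–0.26 SD for completers and 0.12–0.18 SD for the likelihood estimate: a partial correction.

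**Equal rates, 20% v 20%, month-12 link, ρ = 0.5.**
- Same mechanism in both arms: 0.520 × (0.350 − 0.350) = 0.
- Outcome-related in one arm, random in the other: 0.520 × 0.350 = 0.18 SD; simulated type I error 7–12%.
- Low values leave one arm and high values the other: 0.520 × (0.350 + 0.350) = 0.36 SD; simulated type I error 18–33%.

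**Loss unrelated to outcome, after month 3.** Completer bias is about 0. The likelihood estimate has a standard error about 3% smaller (range 1–5%).

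**The case against.** The strongest reply is that this is a small, blinded trial, sized partly on "recommendations for planning pilot studies in clinical and translational research", with no evidence that loss will be large or informative. Section 4.2 M screens out several conditions related to the events monitored in Section 8, and Section 6 reschedules a test rather than discarding it. All of this stands, and it limits how far the concern can be pressed. Pilot status may excuse low power. It does not supply an analysis population, and the plan still makes a two-sided efficacy comparison.

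A second reply is that the proposed model is partly a preference. It adds nothing for a participant with no post-baseline test, and it only partly corrects loss driven by the unseen month-12 value. That also stands, and is why a sensitivity analysis belongs with it.

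A reader might infer more than the text supports:
- That the plan prescribes a completer analysis. It does not: it is silent, and ANCOVA could follow imputation. The restriction arises only because none is planned.
- That participants who stop drug leave follow-up, or that their month-12 values are excluded. Section 3.2 can be read that way, but Sections 6 and 8 do not tie visits to drug use. Both readings remain open.
- That the fasting-glucose rule makes missing tests outcome-related. It governs the test day and reschedules; no such link is shown.

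**Conclusion.** The omission is certain; its effect on this trial is not known. No section gives an analysis population, a method for missing MMTTs or a rule for off-drug values, and the stated month-12 ANCOVA of AUC therefore uses observed month-12 tests only.

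On the assumptions above, with loss after month 3 and linked to the month-3 value, completer bias is about 0.04–0.15 SD, which the likelihood model brings to about 0. Where loss is unrelated to outcome, the gain is only about 3% in standard error. Bias is near 0 if loss is unrelated to outcome, or if both its rate and its mechanism are the same in the two arms. A reader might take similar dropout percentages as reassurance, but equal rates alone do not give it. Nor are these figures an upper limit: they depend on assumed rates, links and timing. The documents do not support a claim that the result will be biased, or in which direction. This is a cheap improvement that should be made.

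**What to change.** 1. **Section 7, primary analysis.** Compare all randomised participants as assigned, using a likelihood-based repeated-measures model of month-3 and month-12 AUC, with baseline AUC as covariate, group-by-visit terms, unstructured covariance and small-sample degrees of freedom. Make the month-12 contrast the primary test. State the limit: bias is removed only when loss is explained by observed baseline and month-3 values.
2. **Section 7, sensitivity analysis.** Add a delta-shift analysis over a stated range that also covers participants with no post-baseline MMTT. A shift of d SD in a fraction f of one arm moves the estimate by f × d; for example, 20% × 0.5 SD = 0.10 SD. Report missing MMTTs by arm and by timing (before or after month 3), with reasons where given.
3. **Sections 3.2 and 4.4.** Reconcile them so that the plan states whether off-drug month-12 values count and what follow-up applies after study drug is stopped, subject to the existing rule on withdrawal for well-being. No continuation rule is proposed here, and either target is defensible.

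The cost is wording and slight extra analysis. Counting off-drug values has a price of its own. If 10–20% of the verapamil arm stopped and lost all benefit (an assumption), the effect would shrink by that share, and equal power would need 1/0.9² = 1.23 to 1/0.8² = 1.56 times the sample.
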